2.1.4 Issues resolved in the analysis datasets

2.1.4.1 ECG/ECHO data

For some patients, ECG/ECHO data was entered mistakenly as unscheduled visits instead of scheduled visits. The algorithms for multiple assessments for quantitative variables will be applied (see [Section 2.1.3](#)). For descriptive analyses for these patients, all data within each scheduled visit window will be taken into account, and the value on the closest day followed

by the worst case will be used. For worst case analyses, the worst case within a time window will be used.

2.2 Analysis sets

The following populations will be used for the statistical analyses:

Enrolled Set (ENR) will consist of all subjects giving study informed consent and are assigned a treatment.

Full Analysis Set (FAS) will consist of all subjects in the Enrolled Set who received at least one dose of study drug. Patients will be analyzed according to the treatment group (as defined in [Section 2.1.1](#)).

Safety Set (SAF) will consist of all subjects in the Enrolled Set who received at least one dose of study drug. Patients will be analyzed according to the actual treatment received (as defined in [Section 2.1.1](#)). The Safety Set will be used for the analyses of safety variables.

Dose Determining Set (DDS) (Part 1 only) will consist of all subjects from the safety set who have sufficient safety evaluations to provide DLT information 2 weeks after the first dosing or discontinue earlier due to DLT. Subjects who do not experience DLT during the first 2 weeks after the first dose are considered to have sufficient safety evaluations if they are considered by both the Sponsor and Investigators to have sufficient safety data to conclude that a DLT did not occur.

PK Analysis Set will include all subjects that received at least one dose of branaplam with available PK data and no protocol deviations with relevant impact on PK data. The PK Analysis Set will be used for the analyses of PK variables.

2.2.1 Subgroups of interest

Subgroup analyses will be performed using descriptive statistics.

The following subgroups will be used for selected efficacy and safety analyses:

- Sex (M/F)
- Baseline Age Group (<= 4 months/> 4 months)

2.3 Subject disposition, demographics and other baseline characteristics

Analyses for subject disposition, demographic characteristics, other baseline characteristics, and medical history, will be summarized by study part for the FAS (and additionally by cohort for Parts 2 & 3) using frequency distributions (for categorical variables) and descriptive

statistics of mean, standard deviation, minimum, median and maximum (for continuous variables). They will also be listed by study part, treatment, and subject. The numbers in each population will be tabulated. Frequencies of protocol deviations will be displayed stratified by deviation category and part.

2.3.1 Subject disposition

The number and percentage of subjects who completed each study part, who prematurely discontinued and the reason for discontinuation will be presented by study part.

2.3.2 Background and demographic characteristics

Summary of baseline demographic characteristics will include:

- Age
- Sex
- Predominant race
- Ethnicity
- Weight
- Length
- Body surface area
- Chest circumference
- Head circumference

Summary of other baseline characteristics will include:

- Mean supine SBP
- Mean supine SBP categories
 - < 130 mmHg
 - >= 130 mmHg
- Mean supine DBP
- Mean supine DBP categories
 - < 80 mmHg
 - >= 80 mmHg
- Mean supine pulse
- Paradoxical breathing assessment,
- eGFR per MDRD formula categories
 - < 30 mL/min/SA
 - >= 30 to < 60 mL/min/SA
 - >= 60 to < 90 mL/min/SA
 - > 90 mL/min/SA
- QTcF

■ [REDACTED]

2.3.3 Medical history

Medical history will be summarized by study part for the FAS (and additionally by cohort for Parts 2 & 3). Any condition entered on the Medical History (MH) CRF will be coded using the MedDRA dictionary. The medical history will be summarized by primary system organ class (SOC), preferred term (PT) and cohort.

2.4 Treatments (study treatment, rescue medication, concomitant therapies, compliance)

The SAF set will be used for the analyses below.

2.4.1 Exposure to study treatment / compliance / time at risk for AE

Duration of treatment exposure in months = (minimum(study day of last non-missing dose (>0) + 6, end of study date, Database cutoff date) - study day of first dose + 1)/30.4375.

Duration of exposure to study drug will be summarized descriptively on the safety set by parts, treatment group and duration category (≥ 1 mos., ≥ 3 mos., ≥ 6 mos., ≥ 9 mos., ≥ 12 mos., ≥ 18 mos., ≥ 24 mos., ≥ 30 mos., ≥ 36 mos., ≥ 42 mos., etc. till no longer any patients).

For each treatment group, the number of patient-years is calculated as (the sum of the number of days of exposure for all patients in the group)/365.25 and will be summarized by baseline age group and gender.

Time at risk for AE is defined as (in months)

- (minimum(study day of permanent study drug discontinuation + 30, study day of end of study part, Database cutoff date, study day of first dose of alternate treatment for SMA) - study day of first dose + 1)/30.4375 (as defined in [Section 2.1.1](#)).

Time at risk for AEs will be summarized in a similar way to duration of exposure to study drug.

Compliance to the study drug administration schedule will be calculated as

- (Number of doses received / number of expected doses up to treatment discontinuation)*100
- Number of doses received = Doses with non-missing dates and a non-missing dose >0
- Number of expected doses = round((study day of last treatment day-1)/7) + 1
- The last treatment date/day is taken from the CMP dataset.
- If number of received doses exceeds the number of planned doses, then compliance = 100% Premature discontinuation from study drug will not be considered non-compliance.

Last treatment day corresponds to the last record of the administration page for parts 1, 2 or 3 with non-missing date for the patient. A dose is received if dose is non-missing and >0.

This rule means that compliance will be measured during the time interval the patient took study drug: premature discontinuation from study drug will not be considered non-compliance. Compliance to study drug administration will be summarized descriptively on SAF by treatment group. In addition, compliance will be summarized with cumulative number and percentage of patients in each compliance category (*i.e.*, $\geq 20\%$, $\geq 30\%$, $\geq 40\%$, $\geq 50\%$, $\geq 60\%$, $\geq 70\%$, $\geq 80\%$, $\geq 90\%$, $\geq 95\%$, $\geq 98\%$, =100%).

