However within 6-7 weeks following implementation of the lower dose of LMI070 as part of the third USM, new safety events, including serious adverse events indicating decrease of motor skills, generalized motor weakness and increased respiratory muscle weakness, occurred in 7 of 10 patients in the ongoing study whose dose was lowered to 6 mg/m². After consultation with Investigators and following recommendations from the internal safety board and as agreed to by the independent DMC, Novartis has decided to institute a fourth USM in response to these clinical events: to re-instate the weekly dose of LMI070 (either 48 mg/m² or 60 mg/m²) that was administered prior to the dose reduction to 6 mg/m² for each patient. The evaluations

implemented in the third USM (additional neurologic and neurophysiologic examinations,

risk/benefit determination by independent physician) remain implemented in the study. Also, as implemented in the third USM, enrollment of new patients remains suspended.

In addition, the following changes have been made to reduce the burden for patients already enrolled in the study:

- Option for safe oral administration of LMI070 to patients who have completed the initial 13 weeks of treatment has been introduced.
- The optional infant cry vital capacity assessment has been removed from Part 1 of the study.
- The number of PK samples taken and their frequency has also been reduced where possible.

At the time this amendment was written thirteen patients have been treated with LMI070 in Part 1 of the study. New information concerning the safety and pharmacokinetics in these patients is provided as part of this amendment.

Changes to the protocol

- Protocol synopsis: changes were made in the synopsis to reflect all changes throughout the protocol as outlined below.
- Figure 1-1: The figure was replaced to reflect a more accurate number of mRNA splicing in SMN2.
- Section 1.1.1.1 has been updated with additional available preclinical information, mainly from the 52-week toxicology study in juvenile dogs.
 - Section 1.1.1.4 and Section 1.1.1.5 have been updated to include the available information from all patients enrolled in Part 1 of the study at time of this amendment.
- Section 2.1 Primary Objective: addition of two following safety endpoints: neurologic examination and neurophysiologic examination following preclinical safety findings in the 52-week toxicology study in juvenile dogs and subsequent implementation of an USM.

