	In Part 1 of the study patients will be dosed once weekly with branaplam until MTD is determined or when sufficient PK results confirm that the Micannot be reached due to a potential pharmacokinetic exposure plateau higher doses. A Bayesian logistic regression model (BLRM) with escalat overdose control (EWOC) will be used to determine the dose levels used for each dose escalation. The decision to dose escalate the next cohort be made after safety data have been collected for 14 days following the dose (14-day DLT window). PK will be used to confirm wash-out of branaplam to avoid accumulation of the compound and to improve understanding of the metabolic pathways of degradation and clearance obtained by the patients of the CYP system. The data will be used to further develop the PK model. If PK data show the potential for accumulation, the dosing frequency may be decreased; For Part 1, patie completing 13 weeks of treatment (12 doses) will be considered to have completed the study. Patients who completed at least 52 weeks of treatment may continue treatment in Part 3 if in the best interests of the patient, as assessed by the investigator. In Part 2 of the study, new patients will be enrolled and will participate for 52 weeks to assess efficacy and safety of branaplam. Patients will be dosed once weekly with branaplam. The decision for starting the next do level cohort will be made after safety and efficacy data have been collect for at least 3 patients treated for 13 weeks following the first dose. Patier completing 52 weeks of treatment will be considered to have completed study. However, they may continue treatment in part 3 of the protocol, if further treatment is in the best interest of the patient. Part 3 of the study is long term safety and efficacy follow up of extended oral/enteral, once a week branaplam treatment. All patients who participated in Part 1 and Part 2 of the study and have completed at least 52 weeks of treatment, or more can continue receiving treatment with branaplam in Part 3 of the st	

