Only patients who meet the inclusion/exclusion criteria at screening will be eligible to proceed to the baseline visit.

For a full list of assessments, please refer to Table 7-1.

Baseline

Visit 2 (Day -7 to -3) and Visit 3 (Day -2 to -1)

Due to the limited blood volumes available in infants, the baseline assessments have been split across two visits. The baseline visit may be combined into one day if appropriate.

All baseline eligibility assessment results must be available and confirmed by the investigator prior to progression into the treatment period.

First dose - Visit 4 (Day 1)

Patients will attend the investigator site in the morning. They will remain at the site for at least 24 hours for safety monitoring, after which they will be discharged locally at the discretion of the investigator. Patients who do not live within 60 minutes travel from the site should be housed locally until the day 8 visit (Visit 8) either at family/friends, or in a hotel. After visit 8 they may return home until their next scheduled study visit.

Pre-dose assessments will be conducted according to Table 7-1.

Time of dosing will be collected in the eCRF and appropriate documentation of the patient specific dispensing process must be maintained. Dose administration should occur at approximately the same time of day at each dosing visit (morning or afternoon). The investigator should be in contact with the Sponsor before dosing to confirm that there is a 24 hour gap between patients receiving their first dose of study drug across all study sites. If two sites have patients scheduled for Visit 4 in the same week, they must be scheduled 24 hours apart, allowing for time zone variations.

Following study drug administration blood samples will be drawn for PK analysis at specified time points throughout the day.

Reflux precautions must be implemented post-dosing per local institutional standards.

For a complete list of assessments, please refer to Table 7-1 for the initial treatment period and to Table 7-2 for the extended treatment period.

PK collections – Visits 5, 6, 7 and 8 (Day 2, 3, 5 and 8)

PK blood collections and safety assessments will be performed per Table 7-1 during the initial treatment period and per Table 7-2 during the extended treatment period and after the transfer into Part 3 per Table 7-4.

Safety Review – Visit 8 (Day 8)

Safety assessments and respiratory function will be performed per Assessment Schedule.

a blood sample for PK will be obtained.

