
Dosing Visits 9 (End of DLT review period) - 19 (Day 15 - Day 85)

If the first dose has been well tolerated during the 14-day DLT review period, patients will continue to be dosed on a weekly basis until end of study, or as long as it is in the best interest of the patient.

Patients will attend the investigator site in the morning. They will be discharged at the discretion of the investigator.

Safety and respiratory function assessments will be performed prior to dose administration per Table 7-1 during the initial treatment period and as per Table 7-2 during the extended treatment period.

Time of dosing will be collected in the eCRF and appropriate documentation of the patient specific dispensing process must be maintained. Dose administration should occur at approximately the same time of day at each dosing visit (morning or afternoon).

Reflux precautions must be implemented post-dosing per local institutional standards.

Patients entering treatment extension will undergo assessments as described in Table 7-2.

End of Study – Visit 777

The End of Study visit will be performed 30 days after the last treatment.

End of study visit will become applicable only when further branaplam treatment is discontinued.

Study completion information is mandatory for this visit and must be completed regardless of the patient's completion / discontinuation status.

All other assessments within this visit should be completed wherever possible, depending on the patient's status and ability to tolerate assessments.

For a complete list of assessments, please refer to the Assessment Schedule.

Patients who are continuing to receive study medication follow the Assessment Schedule - Part 1 - Extended treatment period. The assessment schedule repeats until the patient discontinues the study or transfers to Part 3 of the study.

For patients who completed at least 52 weeks of treatment and who will continue treatment in Part 3, **no** end of study visit needs to be done.

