Screening assessments will be completed per the Assessment Schedule.

To assess eligibility and confirm the diagnosis of SMA, SMN2 copy number will be determined in all patients in whom this has not been previously confirmed. As part of the inclusion and exclusion criteria, hepatitis and HIV screens will also be assessed at this visit. Similarly, general demographics and relevant and current medical history will be recorded.

Monitoring of concomitant medications, adverse events, and serious adverse events will be initiated during this visit.

Only patients who meet all of the inclusion and none of the exclusion criteria at screening will be eligible to proceed to the baseline visit.

For a full list of assessments, please refer to the Assessment Schedule.

Baseline/Randomization

Visit 2 (Day -7 to -3) and Visit 3 (Day -2 to -1)

Due to the limited blood volumes available in infants, the baseline assessments have been split across two visits. The baseline visit may be combined into one day if appropriate.

All baseline eligibility assessment results must be available and confirmed by the investigator prior to progression into the treatment period.

First dose – Visit 4 (Day 1)

Patients will attend the investigator site in the morning.

Pre-dose assessments will be conducted according to the Assessment Schedule.

Time of dosing will be collected in the eCRF and appropriate documentation of the patient specific dispensing process must be maintained. Dose administration should occur at approximately the same time of day at each dosing visit (morning or afternoon).

Following study drug administration blood samples will be drawn for PK analysis at specified timepoints throughout the day.

Reflux precautions must be implemented post-dosing per local institutional standards.

For a complete list of assessments, please refer to the Assessment Schedule.

Dosing Visits 8-67 (Day 8 - 358)

Patients will attend the investigator site in the morning.

Safety and respiratory function assessments will be performed prior to dose administration per the Assessment Schedule.

Time of dosing will be collected in the eCRF and appropriate documentation of the patient specific dispensing process must be maintained. Dose administration should occur at approximately the same time of day at each dosing visit (morning or afternoon).

Reflux precautions must be implemented post-dosing per local institutional standards.

Home Visits

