The study design has adopted a dose escalation design method to originally identify the MTD in **Part 1** similar to that used in oncology studies. Branaplam has known reversible cell-cycle arrest effects at high doses so the study design is planned to monitor and manage such effects (marrow or GI tissue) as delineated from standard pediatric oncology experience. The AE profile anticipated from potential cell-cycle arrest effects are considered to be clinically differential to the type I SMA clinical phenotype. Since Type 1 SMA is fatal, the prospect for direct clinical benefit is a fundamental mandate. In an adult Pharmacodynamic SMA mouse model, it has been demonstrated that a single oral dose of branaplam can drive up SMN protein in the brain and spinal cord and remains elevated for nearly a week. Weekly dosing is implemented after the initial 14-day safety review window, as this is expected to allow for a complete washout between doses. While more frequent dosing may be possible even in Part 1,

our approach is to avoid accumulation until we can be sure that branaplam does not harm patients. Patients will initially be dosed for 13 weeks, however dosing may be extended if recommended by the independent DMC.

PK will be analyzed to complement the safety data acquired. Similar FIH studies have been carried out in infants with fatal illnesses before (Kishnani et al 2007; Worgall et al 2008). It is not practical or ethical to enroll patients into a traditional single dose study and then have them wait potentially 3-6 months until a full cohort is treated at one dose before dose escalation, even with retreatment of the same patients. In that period, a great majority of their vulnerable motor neurons could die off and they would no longer be able to receive potential benefit from branaplam, though they would still be vulnerable to any AE's the drug may cause. We hypothesize that branaplam will rescue alpha-motor neurons from dying, but it is probably not capable of restoring or regenerating lost alpha-motor neurons; thus timing is key for patient entry at early stages of disease for receiving a potentially efficacious dose.

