2.1 Data analysis general information

A statistical vendor (CRO), [REDACTED] to which the statistical analysis is outsourced, will perform all planned analyses, i.e. IAs (Section 2.13) as well as the final analysis after the final database lock. Details of the analyses for Parts 1, 2, and 3 at the upcoming final database lock are outlined in this document.

Data will be analyzed using SAS® version 9.4 (or higher).

Descriptive summary statistics, unless otherwise specified, for continuous variables include number of non-missing observations (n), mean, median, standard deviation (SD), Q1 (25th percentile), Q3 (75th percentile), minimum and maximum, while for categorical variables frequencies and relative percentages will be reported.

Descriptive analyses will be stratified by part as follows:

- For disposition, demographics, baseline characteristics, and medical history, and protocol deviations, by parts (Part 1, Part 2, Part 1 & 2, Part 3)
- For all other summaries and figures: Part 1 & 3, Part 2 & 3, and Total (where applicable)

For analysis summaries, Part 1 will not be stratified by titration dose, while Part 2 will be stratified by the two treatment doses. For patients in Part 3 from Part 2, the fixed dose in Part 2 will be used as a strata; thus transitions from a low dose to a higher dose in Part 3 will not be analysed separately.

Individual graphs, such as spaghetti plots by study part and treatment and panel plots by study part and subject (with actual dose displayed as background shading) relative to time from first dose (in months) will be provided for selected endpoints, as applicable. Individual graphs relative to calendar age (in months) such as growth curve plots of vital signs, etc. will also be presented.

Listings will be provided by study part, cohort and subject.

The following treatment labels will be used for all tables, listings and figures in the order provided here:

- **Part 1:**
LMI070 0.3125 mg/kg, LMI070 0.625 mg/kg, LMI070 1.25 mg/kg, LMI070 2.5 mg/kg,
LMI070 3.125 mg/kg
- **Part 2:**
LMI070 0.625 mg/kg, LMI070 2.5 mg/kg
- **Part 3 (from Part 1):**
LMI070 0.625 mg/kg, LMI070 2.5 mg/kg, LMI070 3.125 mg/kg
- **Part 3 (from Part 2):**
LMI070 0.625 mg/kg, LMI070 2.5 mg/kg

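### The SAP's expected-dose formula counts a Day 8 dose that Part 1 does not schedule, so a Part 1 child dosed exactly on schedule past Day 8 cannot reach 100% compliance

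*SAP*

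**What the plan says.** SAP 2.4.1 defines compliance as doses received divided by doses expected, times 100. A dose counts as received if it has a date and an amount above zero. The expected count is "Number of expected doses = round((study day of last treatment day-1)/7) + 1". If more doses are received than planned, compliance is set to 100%. The last treatment day is taken from the administration records of Parts 1, 2 or 3, and there is no exception for Part 1. Results are tabulated in cumulative categories from at least 20% up to exactly 100%.

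SAP 2.1 sets the columns: "For all other summaries and figures: Part 1 & 3, Part 2 & 3, and Total (where applicable").

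The two dosing schedules differ in the second week:

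- **Part 1 (Protocol 3.1).** The Day 8 visit is headed "Safety Review – Visit 8 (Day 8"), and the next dosing block is "Dosing Visits 9 (End of DLT review period) - 19 (Day 15 - Day 85"). Table 7-1 marks drug administration on Day 1 and on Days 15 to 85, and leaves Day 8 blank. Protocol 3.4 gives the reason: "Weekly dosing is implemented after the initial 14-day safety review window". The protocol summary states the total for children "completing 13 weeks of treatment (12 doses) will be considered to have completed the study".
- **Part 2 (Protocol 3.2).** Dosing after Day 1 is "Dosing Visits 8-67 (Day 8 - 358"), so Day 8 is a dosing day.

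**The concern.** The formula describes the Part 2 schedule and is applied unchanged to Part 1. It expects a Day 8 dose that the Part 1 protocol withholds during the 14-day DLT window. Table 7-2 continues weekly from Day 92, so the extra expected dose is never recovered. The cap does not help, because it acts only when received doses exceed expected doses and here they are one short.

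What is at stake is the reading of the compliance table. Exactly 100% is one of its rows, and Parts 1 & 3 are shown beside Parts 2 & 3. Children who missed nothing would appear fully compliant in one column and not in the other, and a reader would take that for a difference in adherence.

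**Working it through.** **Inputs.** Part 1 dosing days: Day 1, then Days 15, 22, …, 85 (Protocol 3.1, Table 7-1), then weekly from Day 92 (Table 7-2). Part 2 dosing days: Days 1, 8, …, 358 (Protocol 3.2). Expected doses for a last treatment day D: round((D − 1)/7) + 1 (SAP 2.4.1). Here Study Day 1 is taken as the day of first dose.

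**Reproducing the protocol's count.** Day 1 is one dose. Days 15 to 85 in steps of 7 give (85 − 15)/7 + 1 = 11. The total is 12, as the protocol summary states. The SAP formula gives 84/7 + 1 = 13.

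**Compliance for exactly on-schedule dosing**

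| Last dose | Received | Expected (SAP) | Compliance |
|---|---|---|---|
| Part 1, Day 1 | 1 | 1 | 100% |
| Part 1, Day 15 | 2 | 3 | 66.7% |
| Part 1, Day 85 (Week 13) | 12 | 13 | 92.3% |
| Part 1, Day 176 (Week 26) | 25 | 26 | 96.2% |
| Part 1, Day 358 (Week 52) | 51 | 52 | 98.1% |
| Part 1, Day 1324 (Week 190) | 189 | 190 | 99.5% |
| Part 2, Day 85 | 13 | 13 | 100% |
| Part 2, Day 358 | 52 | 52 | 100% |

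Past Day 8 the Part 1 score is (N − 1)/N, where N is the formula's count. It reaches 90% from a last dose in Week 10 (9/10), 95% from Week 20 (19/20) and 98% from Week 50 (49/50). It never reaches 100%.

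**Who is affected**

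- Amendment 05 (August 2016) reports: "At the time this amendment was written thirteen patients have been treated with LMI070 in Part 1 of the study". Amendment 7 (December 2017) reports 8 children ongoing. From 31 August 2016 to 1 December 2017 is 457 days, or 65.3 weeks. Those 8, if on schedule, score at least 65/66 = 98.5% and miss only the =100% row.
- The other 13 − 8 = 5 could also miss the 98% row (last dose before Week 50) or the 95% row (last dose before Week 20). Their individual exposure is not given.
- Amendment 05 describes a dose reduction for children who had completed 13 weeks, and 10 children had their dose lowered. A score of 92.3% or less can therefore apply to at most 13 − 10 = 3.

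**Illustration of the table.** If all 38 treated children were exactly on schedule past Day 8 (an assumption), the =100% row would read 0/13 in Parts 1 & 3, 25/25 in Parts 2 & 3, and 25/38 = 65.8% in a Total column if one is produced.

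**Sensitivity to timing.** A last dose four or more days early hides the gap: Day 81 in place of Day 85 gives round(80/7) + 1 = 12, which equals the 12 received.

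**Side check on Study Day.** SAP 2.1.1 counts Study Day from treatment assignment, while the exposure formula in 2.4.1 subtracts the study day of first dose. An assignment 0 to 3 days before first dose leaves the expected count unchanged. An assignment 4 to 10 days before adds one more (at Day 85: Part 1 12/14 = 85.7%, Part 2 13/14 = 92.9%). A 1- or 2-day lead would also put a first-dose-day ECG outside the Day 1 window (1 to 1) of SAP Table 2-5. The documents do not state the interval, so this is a consistency point and not a demonstrated error.

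**The case against.** The strongest reply concerns size.

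- **The low percentages apply only to early stoppers.** Compliance runs to the last administration record, Part 3 included. A child on schedule from the end of August 2016 to Amendment 11 (19 July 2021) has 1,783 days, or 254 full weeks, and scores 254/255 = 99.6%. Protocol 1.1.1 also says that worsening after the dose reduction led or contributed to five deaths. If those five are the children no longer ongoing in December 2017, none is at 92.3% or below. The deaths are not dated, so this is possible but not shown.
- **The =100% row is not a clean adherence marker in either part.** Dose suspensions required by Protocol Table 5-7 count as missed doses under the same formula, so a Part 2 child who follows the protocol can also fall short.
- **Departures from the exact schedule can mask the gap.** An early last dose does so, and so could a repeat dose after vomiting if it is recorded separately.
- **Nothing depends on the table.** The study is non-confirmatory, compliance is not an endpoint, and the error understates compliance. The dosing listing and dosing timelines keep the actual doses.

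All of this limits the consequence and supports a low rating. None of it removes the error. The formula still expects a dose that the Part 1 schedule leaves out, and no Part 1 exception appears in the SAP. The 0/13 against 25/25 comparison should be read as an illustration under a strong assumption, and SAP 2.4.1 itself asks only for summaries by treatment group, so a Total column may not appear.

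**Conclusion.** The concern holds, as a minor point. Followed exactly, SAP 2.4.1 gives an expected count that is one too high for every Part 1 child dosed on schedule past Day 8. The shortfall is 7.7 percentage points for a child whose last dose is on Day 85 (100 − 92.3), 1.9 at Week 52 and 0.5 at Week 190. It reaches a category other than =100% only for children who stopped before Week 50, at most 5 of the 13 if the 8 continuing children were on schedule. The percentages assume exact adherence to the visit plan and a study day counted from first dose. No efficacy or safety conclusion depends on them. The Study Day wording carries no weight in this conclusion.

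**What to change.** In SAP 2.4.1, define expected doses as round((last treatment date − first dose date)/7) + 1, less 1 for children who entered in Part 1 and whose last treatment date is after Day 8, with Day 1 as the day of first dose. For on-schedule Part 1 dosing this gives 1/1 at Day 1, 2/2 at Day 15, 12/12 at Day 85 and 51/51 at Day 358. Part 2 stays at 52/52.

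For consistency, also define Study Day 1 in SAP 2.1.1 as the date of first dose. This changes nothing if assignment and first dose fall on the same day.

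The cost is one line of SAP text and a re-derivation of compliance for the 13 Part 1 children, plus a second line for Study Day. Neither change touches dosing or data collection.
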